5. EFFICACY

All efficacy data will be analyzed by intervention arm, analysis phase and over time (when applicable). The primary analysis set will be the mITT analysis set (see definition in Section 2.3). Selected efficacy endpoints will be also analyzed using the ITT, and PP analysis sets, respectively (see definition in Section 2.3). Efficacy assessments over time will be performed at the analysis time points defined in Section 2.1.

5.1. Analysis Specifications

All efficacy endpoints will be summarized descriptively by study intervention arm. In general, continuous variables will be summarized using descriptive statistics (for example, may include the number of participants, mean, standard deviation (SD), 90% confidence interval (CI), median, and range). Binary or categorical variables will be summarized using the number and percentage of participants in each category. For time-to-event variables, a summary table including number of participants included in the analysis, number of participants censored, 25th and 75th percentiles and median time-to event will be shown. Descriptive summaries may be presented by the 2 randomization stratification factors, HBeAg status at screening and treatment history for the primary and key secondary endpoints and selected other secondary endpoints. Graphic displays will also be used to summarize the data.

5.1.1. Level of Significance

The study addresses two separate research questions:

- 1) Dose finding: the comparisons of 3 doses of JNJ-3989+NA (Arms 2, 3, and 4) against NA treatment alone (Arm 6) and other comparisons of active regimens (Arm 1 and Arm 5) vs Arm 6,
- 2) Regimen finding: the comparisons of the combination regimen of JNJ-3989 (100 mg) +JNJ-6379 +NA (Arm 1) vs each of the mono components JNJ-3989 (100 mg) and JNJ-6379, respectively, on the background of NA (Arm 3 and Arm 5).

For the primary efficacy endpoint analysis, the Type 1 error rate is controlled at 0.05 one-sided level for multiple comparisons within each separate research question differently and independently.

For the comparisons against the control, a fixed sequence approach is used where the first step implements the multiple contrast test of the MCP-Mod methodology (applied to Arms 2, 3, 4, and 6) to detect a trend test among the JNJ-3989 doses (40 mg, 100 mg and 200 mg), under the null hypothesis of no differences across the four arms, which is followed by the pairwise comparison of Arm 1 vs Arm 6, followed by the pairwise comparison of Arm 5 vs Arm 6. Based on the fixed sequence principle, each step must be found statistically significant at a one-sided 0.05 level in order to proceed to the next step.

For the comparisons among the regimens (Arms 1, 3, and 5), the min test principle is used. The JNJ-3989+JNJ-6379+NA combination regimen Arm 1 will be declared statistically superior to the dual regimens (Arm 3 and Arm 5) if both tests of Arm 1 vs Arm 3 and Arm 1 vs Arm 5 demonstrate statistical significance at the one-sided 0.05 level.

For the key secondary endpoint, the same multi-step testing strategy as the one implemented for the primary efficacy endpoint described above, using MCP-Mod and additional treatment arms pairwise comparisons against control in a fixed sequence, as well as the min test approach separately for between-regimen comparisons, will be used for this key secondary endpoint. However, the comparisons with NA control in the testing strategy applied to this efficacy endpoint will be made against the NA historical control benchmark of 5%, instead of the study NA control arm (Arm 6).

For the key secondary efficacy endpoint (functional cure at week 72), the tests to compare the JNJ-3989+JNJ-6379+NA regimen against the JNJ-3989+NA and JNJ-6379+NA combination regimens, respectively, will be performed at a one-sided 0.025 alpha level. This more stringent significance level aims to support for regulatory consideration the selection of the combination regimen to be studied in confirmatory studies.

All other efficacy analyses will be based on one-sided alpha level of 0.05, and/or 90% confidence interval (CI) will be presented, with no multiplicity adjustment, unless otherwise specified.

5.1.2. Data Handling Rules

Those measurements collected from screening visit to the end of study will be handled according to the following rules summarized in [Table 3](#).

Table 3: Data Handling Rules for HBV Virology and Serology Assessments

HBV parameter	LLOQ	ULQ	Imputed Values	
			If value < LLOQ ULQ	If value >
HBsAg	0.05 IU/mL	124,925.00 IU/mL w/o dilution 249,750.00 IU/mL with dilution	0.025 IU/mL ^(a)	137,417.50 IU/mL w/o dilution ^(b) 274,725.00 IU/mL ^(b) with dilution
HBeAg	0.11 IU/mL	1,400.00 IU/mL w/o dilution 7,000.00 IU/mL with dilution	0.055 IU/mL ^(a)	1,540.00 IU/mL ^(b) w/o dilution 7,700.00 IU/mL ^(b) with dilution
HBcrAg	3.0 Log ₁₀ U/mL	7.0 Log ₁₀ U/mL w/o dilution 9.0 Log ₁₀ U/mL with dilution	2.7 Log ₁₀ U/mL	7.7 Log ₁₀ U/mL ^{(b)(c)} w/o dilution 9.9 Log ₁₀ U/mL ^(b) with dilution
HBV DNA	20 IU/mL	170,000,000 IU/mL w/o dilution	If target detected: 15 IU/mL If target not detected: 5 IU/mL	187,000,000 ^{(b)(c)} w/o dilution
HBV RNA*	LLOQ = 4.04 log ₁₀ cp/mL LOD = 2.49 log ₁₀ cp/mL	NAP	If < LOD or target not detected then 2.19 log ₁₀ cp/mL	NAP
Anti-HBs	5mIU/mL	10000.0 mIU/mL	2.5 mIU/mL ^(a)	11000.0 mIU/mL ^(b)

* As new assays become available different data handling rules may apply

Key: NAP=Not applicable

(a) LLOQ/2

(b) ULOQ+(ULQ/10)

(c) If the original result >ULQ then take the re-test value (i.e. diluted result). If the diluted result is not available, use the imputed value indicated in this table.

All other viral activity data with values <LLOQ which are not included in the data handling rules above will be imputed by the absolute value divided by 2.

5.2. Primary Efficacy Endpoint

5.2.1. Definition

The primary efficacy endpoint is defined as the proportion of participants meeting the NA treatment completion criteria **at Week 48**.

A participant will be defined as responder in meeting the NA treatment completion criteria at Week 48, if the following criteria are met based on the clinical laboratory tests performed **at Week 44**:

- ALT <3x upper limit of normal (ULN), AND
- HBV DNA <LLOQ, AND
- HBeAg-negative (<LLOQ), AND
- HBsAg <10 IU/mL.

Note: In case of ALT elevation $\geq 3x$ ULN at Week 44, the ALT re-test before Week 48 may be performed. If the ALT re-test meets the criteria above, the participant will be considered as responder as satisfying the NA treatment completion criteria.

Note: Quantitative HBeAg assessment is only performed at Week 44 for participants who are HBeAg positive at screening. Therefore, if a participant is HBeAg negative at screening, they are assumed to be negative at Week 44 for the purpose of the primary endpoint.

5.2.2. Main Estimand for The Primary Endpoint

Primary Study Objective: To establish the dose-response relationship for antiviral activity of 3 doses of JNJ-3989+NA and to evaluate the efficacy of combination regimens of JNJ 3989+NA (with and without JNJ-6379) and of JNJ-6379+NA.

Scientific question: in the adult population with chronic HBV infection

- a) what is the benefit of any of the JNJ-3989 doses (40mg, 100mg or 200 mg) (Arms 2-4) administered in combination with NA for 48 weeks in terms of antiviral HBV replication and liver inflammation compared with Placebo+NA?
- b) what is the benefit of JNJ-3989 100 mg+JNJ-6379+NA (Arm 1) and JNJ-6379+NA (Arm 5) for 48 weeks in terms of antiviral HBV replication and liver inflammation compared with Placebo+NA?
- c) what is the benefit of JNJ-3989 100mg+NA with or without JNJ-6379 (Arm 1, 3) or JNJ-6379+NA (Arm 5) administered for 48 weeks in terms of antiviral HBV replication and liver inflammation?

A) The primary estimand for the primary endpoint is characterized by the following attributes:
Study Intervention:

- Arm 1: JNJ-3989 (100 mg) + JNJ-6379 (250 mg qd) + NA
- Arm 2: JNJ-3989 (200 mg) + Placebo + NA
- Arm 3: JNJ-3989 (100 mg) + Placebo + NA
- Arm 4: JNJ-3989 (40 mg) + Placebo + NA
- Arm 5: Placebo + JNJ-6379 (250 mg qd) + NA

- Arm 6: Placebo + Placebo + NA

B) Study Population: HBeAg-positive and -negative chronic HBV-infected patients who are not being treated for their HBV infection (including treatment-naïve participants) or are virologically suppressed by being treated with NA.

C) Variable: Response status defined as meeting the NA treatment completion criteria (responders) at Week 48 as defined in Section 5.2.1.

D) Intercurrent events:

- Treatment discontinuation prior to Week 48:
 - if the participant discontinued treatment prior to Week 44, then s/he will be considered non-responder (composite strategy).
 - if the participant discontinued treatment between Week 44 and Week 48 but ALT, HBV DNA, HBeAg (only for the participants with HBeAg positive status at baseline), and HBsAg assessments for primary endpoint are available, all data will be used regardless of occurrence of the intercurrent event (treatment policy strategy).
- Major protocol deviations affecting efficacy: [ATTACHMENT 1](#) identifies the deviations considered intercurrent event (in the Per Protocol set 1 column [PP1] for the primary efficacy endpoint). Participants with such deviations and who have missing data for the primary endpoint at Week 48 will be considered as non-responders (composite strategy). For all other deviations not considered intercurrent events, the data are used regardless of the occurrence of major protocol deviations (treatment policy strategy).
- Deaths prior to Week 48 are handled in a composite strategy as participants who die prior to Week 48 will be considered as non-responders.

E) Population-level summary: Difference in proportion of responders at Week 48 between study intervention arms.

5.2.2.1. Main Estimator

5.2.2.1.1. Analysis Methods

5.2.2.1.1.1. Scientific Question Part a: JNJ-3989 Dose Response Trend Test and Dose Response Model Estimation

[figure not shown]
Statistical Model: For the JNJ-3989 dose-finding objective, a hybrid methodology that combines aspects of multiple testing with modeling techniques (MCP-Mod) will be used for evaluating a dose-response trend and estimating the dose-response relationship of 3 JNJ-3989 doses in combination with NA (Arm 2, 3 and 4) versus NA treatment alone (control Arm 6). Because the primary efficacy endpoint is binary, the generalized MCP-Mod approach ([Pinheiro J. et al, 2014](#)) will be used on the logit scale. Following the notation in Pinheiro et al (2014), the “dose-response parameter” estimates and their variance-covariance matrix will be obtained from a logistic regression with JNJ-3989 dose treated as a factor, where Arm 6 corresponds to “JNJ-3989 dose=0

mg”. The Firth's penalized likelihood method (Firth D., 1993 & Heinze G. et al., 2002) will be used in the logistic regression to reduce possible bias which could arise in the presence of a zero response rate at one or more dose levels

If one or more prespecified models are found to be significant (multiple contrast test approach), a significant trend test among Arms 2, 3, 4, and 6 (JNJ-3989 40 mg, 100 mg and 200 mg and NA control), under the null hypothesis of no differences across the 4 arms will be declared.

A set of 5 candidate models (see [Figure 1](#)) was prespecified as possible dose-response shapes in terms of the logit of the primary efficacy endpoint. The 5 candidate models are the EMax1 (ED₅₀=5 mg), EMax2 (ED₅₀=100 mg), Linear, Exponential (d=40) and Sigmoid Emax model (ED₅₀=110 mg, h=8). A dose-response trend is established when the maximum of the t-test statistics exceeds the critical value at the one-sided 0.05 alpha.

Figure 1: Candidate Dose-response Models on the Logit Scale

Characterization of the dose-response model: The model averaging techniques (Bornkamp B. et al., 2009) across the candidate models will be utilized to derive the dose-response shape and to evaluate the desired dose(s) of JNJ-3989 (modeling step). The estimated dose response curve and the corresponding 90% confidence band will be plotted against the JNJ-3989 dose range of 0 mg to 200 mg.

5.2.2.1.1.2. **Scientific Question Part b: Pairwise Comparisons vs Control Arm**

After a positive significant dose-response signal is established for the combination regimen JNJ-3989+NA, the testing procedure continues in a fixed sequence to control the type 1 error in presence of multiple testing, with the comparison of Arm 1 (JNJ-3989+JNJ-6379+NA) with control Arm 6 at a one-sided alpha of 0.05. If Arm 1 is found statistically superior to control Arm 6, then the combination regimen JNJ-6379+NA (Arm 5) is compared to control Arm 6 at 0.05 one-sided alpha level. The Mantel-Haenszel (MH) test (Mantel N. et al., 1959) for the difference of 2 proportions adjusted for the 2 randomization stratification factors (treatment history

status and screening HBeAg status) will be used at one-sided 0.05 alpha level in each of the above mentioned pairwise comparisons.

5.2.2.1.1.3. Scientific Question Part c: Comparisons Among Combination Regimens

For the regimen-finding objective, the statistical comparisons among the regimens (Arm 1, 3, and 5) will be performed using the min test approach to control for the Type I error rate at the one-sided 0.05 alpha level. The JNJ-3989+JNJ-6379+NA combination regimen will be declared statistically superior to the dual regimens if both tests of Arm 1 vs Arm 3 and Arm 1 vs Arm 5 demonstrate statistical significance at the one-sided 0.05 level. The Mantel-Haenszel test for the difference of 2 proportions adjusted for the 2 randomization stratification factors will be applied.

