JNJ-3989 was generally safe and well tolerated with no deaths, serious adverse events (SAEs) considered at least possibly related to the study intervention, or adverse events (AEs) leading to study intervention discontinuation. All AEs were mild to moderate, with exception of 1 severe blood creatine phosphokinase increased in 1 CHB participant. All reported injection site reactions (ISRs) were mild. Adverse events and laboratory abnormalities were distributed across all dose levels and also occurred on placebo treatment, except for mild ISRs, which were only reported in participants on JNJ-3989 treatment. Most reported laboratory abnormalities were isolated incidences and resolved while on study treatment.

Efficacy was assessed using snapshot data through 02 May 2019. Antiviral activity data were available for 56 CHB participants who received 3 subcutaneous injections of 25 to 400 mg JNJ-3989 every 4 weeks. The antiviral activity data showed that administration of JNJ-3989 at doses of 25 to 400 mg resulted, on average, in pronounced HBsAg decline which was generally sustained at least until Day 168 (ie, 16 weeks after last dose) across all doses. No apparent dose response was observed at doses between 100 and 400 mg JNJ-3989; a reduced mean decline was observed at the lower dose of 25 mg. Data on the 50 mg dose were still emerging at the time of protocol writing. Treatment status (ie, virologically suppressed or not treated) did not seem to affect HBsAg changes. Other measurable serological and virological markers (HBV DNA, HBV RNA, HBeAg, hepatitis B core-related antigen [HBcrAg]) also showed responses to JNJ-3989, indicating that JNJ-3989 shows target activity on all detectable viral products.

JNJ-6379

At the time of protocol writing, 98 adult healthy and 41 CHB participants have been dosed with JNJ-6379 in 4 completed Phase 1 studies (56136379HPB1001, 56136379HPB1002, 56136379HPB1003, and 56136379HPB1004). Another Phase 1 study in healthy participants is also completed and clinical study report writing is currently ongoing (56136379HPB1005). In addition, data are available from 148 participants in the ongoing Phase 2a study, 56136379HPB2001, also referred to as Jade.

Human Pharmacokinetics and Product Metabolism

Single Dose Studies in Healthy Participants

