3.1. Interim Analyses

The primary analysis will be conducted at the time when all participants have completed Week 48 or discontinued earlier.

Interim analyses will be conducted to monitor safety and evaluate the time course of different disease markers to support the sponsor's internal decision-making, interactions with health

authorities, as well as inform decisions about additional studies and/or investigation of other treatment combinations. Three IAs are planned when:

- All participants have completed Week 60 visit or discontinued earlier.
- All participants have completed Week 72 visit or discontinued earlier.
- All participants have completed Week 96 visit or discontinued earlier.

One additional IA may be performed at the sponsor's discretion when all participants, who completed NA treatment at Week 48 of follow-up, have completed Week 120, i.e. Week 24 of the extended follow-up, or discontinued earlier. As all IAs follow the primary analysis, they will be conducted by the sponsor. Both primary and interim analyses will be based on all data available at the predefined cut-off time, including data at later time points for those participants who have reached subsequent visits

The final analysis will be performed when all participants have completed the last study visit or discontinued earlier.

This SAP covers the definitions of analysis sets, derived variables and statistical methods for the primary, interim and final analyses of this study.

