5.2.2.2.1. Sensitivity Estimator 1 For the Main Estimand (Homogeneity Assumption)

Homogeneity will be assessed for scientific question part b, comparison vs control arm. For this sensitivity estimator 1, the same included data, missing data assumption (MAR), and missing data handling rule (multiple imputation) as well as the same approach to control the Type I error rate (Section 5.1.1) will be applied. The assumption for homogeneity of treatment effect across the stratification factors will be tested and, if heterogeneity is found statistically significant, a different statistical model is used to define the sensitivity estimator.

5.2.2.2.1.1. Assumptions

- Missing Data for HBV RNA, ALT, and HBsAg are Missing at Random
- The treatment effect is non-homogeneous across strata

5.2.2.2.1.2. Analysis Methods

Homogeneity of treatment effect for each stratification factor separately will be tested using the weighted least squares chi-squared statistic (Lui K. J. et al., 2000) for one-way homogeneity. Tests of homogeneity will be assessed at the one-sided 10% level of significance.

Any heterogeneity found to be statistically significant will be explored using the following statistical model for the sensitivity estimator 1.

Statistical model: A logistic regression model on the primary efficacy endpoint using the 2 randomization stratification factors and interaction terms. The model will include intervention arm, treatment history status and HBeAg status at screening as factors, and the intervention arm-by-factor interaction terms.

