5.3.4.1. Main Estimator

To assess the functional cure rate against the observed proportion in the control Arm 6, for this estimator, the same statistical model (MCP-Mod, and stratum-adjusted MH test), data included, assumptions, and MI approach for handling missing data and approach to control the Type I error rate will be used as for the main estimator of the main estimand for the primary endpoint (Section [5.2.2.1](#)). The MCP-Mod approach and pairwise statistical tests to compare with control will be based on the data from Arm 6 instead of historical control fixed value of 5%. The MCP-step will use the actual data from Arm 6, and statistical test to compare Arm 1 and Arm 5 to control will be the MH test as it compares 2-sample proportions.

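### The MCP-Mod trend test that gates the control comparisons omits both randomisation factors: valid, but modest power is forgone and no sensitivity estimator covers it

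*SAP*

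**What the plan says.** The dose-response estimates and their covariance are "obtained from a logistic regression with JNJ-3989 dose treated as a factor", fitted by Firth's penalised likelihood, with Arm 6 as dose 0 (SAP 5.2.2.1.1.1). No covariate is named. The pairwise comparisons in SAP 5.2.2.1.1.2 and 5.2.2.1.1.3 use a Mantel-Haenszel test "for the difference of 2 proportions adjusted for the 2 randomization stratification factors". The trend test comes first in the sequence against control, followed by Arm 1 vs 6 and then Arm 5 vs 6, and "each step must be found statistically significant at a one-sided 0.05 level in order to proceed to the next step" (SAP 5.1.1).

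On strata, the SAP offers Sensitivity Estimator 1, with this scope: "Homogeneity will be assessed for scientific question part b, comparison vs control arm". Part a, the trend test, is outside it. Sensitivity Estimators 2 and 3, the ITT estimators (5.2.2.3) and Supplementary Estimand 1 (5.2.3) keep the same MCP-Mod model. They change only the missing-data handling, the intercurrent-event rule or the analysis set.

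**The concern.** The trial randomises by two factors, uses them in every pairwise test of the primary endpoint, and leaves them out of the one test that everything against control depends on. SAP Amendment 1 dropped the Wilson interval because it ignores the stratification factors. That reasoning was not carried over to the trend test, and no reason is given.

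HBeAg status is plausibly prognostic by construction: "if a participant is HBeAg negative at screening, they are assumed to be negative at Week 44", so those participants start with one of the four response criteria met. Treatment history is less certain. In the earlier study treatment status "did not seem to affect HBsAg changes" (Protocol 2.2.1). But the endpoint also requires HBV DNA below LLOQ and ALT below 3x ULN, and the two groups enter with very different values of both (Protocol 5.1).

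If the factors are prognostic, stratified randomisation has already removed part of the between-arm variability, and the dose-only model still counts it as noise. The cost falls where the design is weakest: an early plateau and a top-dose rate below 25%.

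**Working it through.** **Inputs from the documents.** n = 45 (Arm 6) and 90 in each of Arms 4, 3 and 2; control rate 5%; top-dose rates 25% and 20%; one-sided 0.05; five candidate shapes (Protocol 9.2 and Table 6, SAP 5.1.1 and 5.2.2.1.1.1). Stratum mix: 40% not currently treated, 40% of them HBeAg-positive, so 0.4 × 0.4 = 16% and 0.4 × 0.6 = 24%.

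**Assumed.** 30% HBeAg-positive among the suppressed 60%, giving 18% and 42%. Odds ratios (OR) for response in HBeAg-positive and in not-treated participants, varied below. The documents give neither.

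**Test.** With one factor, the Firth estimate per dose is log[(y + 0.5)/(n − y + 0.5)], with variance 1/[n p(1 − p)] and p = (y + 0.5)/(n + 1). For each shape m, the optimal contrast is c = S⁻¹(m − m̄1), where S is the estimated covariance and m̄ the S⁻¹-weighted mean. The statistic is c'θ/√(c'Sc). Reject if the largest of the five exceeds the 95% point of the maximum under the multivariate normal.

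**Adjusted version.** Firth logistic regression with dose, HBeAg status and treatment history. Standardise: p_d = Σ w_s expit(a_d + b_E e_s + b_T u_s) over the observed stratum shares w_s, take θ_d = logit(p_d), and use a delta-method covariance. The conditional version uses the a_d directly.

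**Reproducing the plan.** For Emax with ED50 = 5 mg, dose-only power without stratum effects is 0.855 at 25% (Table 6: 0.851) and 0.551 at 20% (Table 6: 0.582). So the stated 85% rests on the unadjusted test. Some other cells match less closely: a separately coded run gave 0.927 against 0.953 for Emax ED50 = 100 at 25%. The contrast and variance choices behind Table 6 are not documented.

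**Effect of adjustment**, Emax ED50 = 5, 10,000 trials per row, same simulated trials for all methods (Monte Carlo SE at most 0.005 per power):

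| HBeAg-positive OR / not-treated OR | 25%: dose-only | standardised | gain, points | 20%: dose-only | standardised | gain, points |
|---|---|---|---|---|---|---|
| 1 / 1 | 0.855 | 0.859 | 0.4 | 0.551 | 0.562 | 1.1 |
| 0.5 / 1 | 0.854 | 0.861 | 0.7 | 0.554 | 0.569 | 1.5 |
| 0.2 / 1 | 0.852 | 0.864 | 1.2 | 0.556 | 0.581 | 2.5 |
| 0.1 / 1 | 0.856 | 0.872 | 1.6 | 0.555 | 0.587 | 3.2 |
| 0.2 / 0.5 | 0.859 | 0.876 | 1.7 | 0.558 | 0.591 | 3.3 |
| 0.2 / 0.2 | 0.860 | 0.886 | 2.6 | 0.551 | 0.603 | 5.2 |
| 0.05 / 0.05 (extreme) | 0.871 | 0.911 | 4.0 | 0.560 | 0.645 | 8.5 |

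Conditional log-odds contrasts gain more: 0.5 to 5.2 points at 25% (8.1 in the extreme row) and 1.5 to 10.7 at 20% (18.7). The separately coded simulation (4,000 runs) gave 0.859 to 0.885 standardised for 0.2 / 0.2 at 25%, the same 2.6 points.

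**Other shapes**, 25%, HBeAg OR 0.1, dose-only to standardised: Emax ED50 = 100, 0.932 to 0.941; linear, 0.976 to 0.979; sigmoid Emax, 0.992 to 0.993; exponential, 0.996 to 0.997.

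**HBeAg-positive share among suppressed** (HBeAg OR 0.1): at 15% or 50%, the standardised gain is 1.2 or 2.6 points at a 25% top rate and 2.4 or 4.2 at 20%. In the separately coded run (ORs 0.2 / 0.5, 25% top rate), shares of 10% and 50% gave only 0.5 and 0.6 points, against 1.6 at 30%. Rounding stratum counts there left the control mix slightly different from the dosed arms. The exact gain should not be relied on.

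**Type I error** at a flat 5% rate: 0.011 to 0.014 dose-only, 0.014 to 0.015 adjusted. At a flat 15% rate with no stratum effect the dose-only test is at 0.025. Low event counts (0.05 × 45 = 2.25 expected control responders) explain most of the conservatism, and adjustment does not remove it.

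**The case against.** The strongest reply is that this is a preference. The dose-only test is valid, meets its stated power, and targets the marginal logit on which the candidate shapes are defined; simply adding covariates would change that scale. All of this stands, and it is why the adjusted version has to be standardised.

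Second, the gain is assumed. With HBeAg as the only prognostic factor, it is 0.7 to 1.6 points at the design point. It is 0.4 points even when the strata do not matter, so not all of it comes from prognosis. That stands as a limit on size. A stronger form says that matching the adjusted test's size to the dose-only test removes the gain: 0.862 to 0.879 became 0.854 after matching at a flat 5% null, a calibration resting on about 100 rejections. This does not carry. Both tests stay well below 0.05, and part of the dose-only test's conservatism is the overstated variance itself. At a flat 15% rate in the separately coded run, dose-only size falls from 0.026 with no stratum effect to 0.014 at ORs of 0.1 / 0.1, while the standardised test moves only from 0.027 to 0.026. Recovering that is real power at the nominal level.

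Third, adjusted logistic models already exist in Protocol 9.4.1.1 and SAP 5.2.5. Neither is a trend test, and the SAP one uses observed cases only.

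Fourth, a sensitivity estimator added after unblinding recovers no power at the gate. That is correct. Its use then is to show whether the gating result depends on ignoring the strata.

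**Conclusion.** The point holds as one of efficiency and consistency, not error. The gating trend test is dose-only, the pairwise tests are stratum-adjusted, and no sensitivity estimator bridges the two. On the recommended standardised scale, the power forgone under the weakest candidate shape is about 0.4 to 2.6 points at a 25% top-dose rate and 1.1 to 5.2 at 20%. It is larger only under extreme stratum effects and below 1 point for the other four shapes at 25% (HBeAg OR 0.1). These sizes rest on assumed stratum odds ratios and an assumed HBeAg-positive share among suppressed participants. The absence of stratum terms is read from the SAP naming dose alone. Type I error and the stated 85% power are not in question.

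**What to change.** Fit the Firth logistic regression with dose, screening HBeAg status and treatment history as main effects. Standardise the fitted probabilities over the observed strata to one marginal logit per dose, with a delta-method covariance, and use these for both the MCP and the Mod step. Both steps then stay on the response-rate scale of the candidate shapes and the plotted curve, at the price of a smaller gain than conditional log-odds would give. Do the same in Supplementary Estimand 2 of the key secondary endpoint (SAP 5.3.4.1), where "The MCP-step will use the actual data from Arm 6".

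Timing decides its status. SAP Amendment 2 refers to interim analyses already done, and SAP 3.1 states: "As all IAs follow the primary analysis, they will be conducted by the sponsor". If the primary analysis is unblinded, add this as a labelled sensitivity estimator for part a and leave the prespecified dose-only test as the gate; replacing the gate then would be post hoc. Only in a version fixed before unblinding should it be the main model.

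The cost is two model terms and a standardisation step, repeated in each imputed data set and in the bootstrap of the Mod step. The imputation models in SAP 5.2.2.1.4 already include both factors, so no new data are needed.
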